Chemistry, hematology, urinalysis		X		X ⁵	X ⁵	X ⁵	X ⁵ (no urinalysis)	X	
ECG		X		X				X	
Vital Signs		X	X	X	X	X	X (unless remote)	X	
Plasma for PK ⁶			X	X	X	X			
Pregnancy Test ⁷		X						X	
ECOG Performance Status Assessment		X			X	X		X	
WOMAC Questionnaire ⁸			X	X	X	X	X (unless remote)	X	
Numeric Rating Scale (NRS) for PVNS Symptoms Questionnaire to Patient ⁸			X	X	X	X	X (unless remote)	X	
Dispense Numeric Rating Scale (NRS) for PVNS Symptoms Questionnaire for Outpatient Completion ⁹		X		X	X	X	X (unless remote)		
Serum and Urine for Biomarker Assessment ¹⁰			X		X				
Radiographic Assessment of Tumor Burden ¹¹		X				X	X (every 6 months)	X	X
Test Article Compliance			X	X	X	X	X (unless remote)	X	
Concomitant Medications		X	X	X	X	X	X	X	
Adverse Events ¹²			X	X	X	X	X	X	
Collection of surgical data ¹³								X	X

C = cycle; D = day; CxDx = Cycle x, Day x; LD = last dose; wk = week

- ¹ Screening window for radiographic assessment of tumor burden is 4 weeks.
- ² If well tolerated and no tumor progression; clinic visits, laboratories at 1-month intervals with radiographic assessment performed every two cycles. Radiographic assessment of tumor status can be performed every four cycles in patients who complete 14 cycles of treatment (i.e., reached Cycle 15 visit) and have Cycle 13 and Cycle 15 MRI scans that indicate SD or better per local RECIST v1.1 reading. For patients beyond Cycle 40, clinic visits will transition to every 12 weeks/3 cycles (remote serum chemistry and hematology as well as a telephone check-in for AEs and con meds and to review remote safety laboratory data may be performed in lieu of an on-site visit for subjects without ongoing Grade 2 or greater related adverse events; regular procedures not performed remotely include Weight, PE, Vitals, WOMAC, NRS, and IP compliance), with on-site visit and radiographic assessments performed every 24 weeks/6 cycles.
- ³ End of Study or early withdrawal procedures should be completed 7-30 days after the last dose of study drug (or on the date of last dose of study drug for all subjects that enroll in the phase 4 continuation study) and prior to the initiation of any new anti-cancer therapy. If patient is starting commercially available drug then the end of study visit should be conducted before that transition.

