14.7.1 Renal Impairment

A reduced dose of 600 mg/day (200 mg in the morning and 400 mg in the evening) is recommended in study subjects with mild to severe renal impairment (creatinine clearance [CL_{cr}] 15 to 89 mL/min estimated by Cockcroft-Gault using actual body weight).

14.8 End of Study/Early Withdrawal (last dose for subjects that enroll in phase 4 continuation study or immediately transition to commercial pexidartinib; last + 30 ± 7 days for all other subjects)

Note: In order to be eligible to participate in the phase 4 PVNS continuation study, subjects must not be withdrawn from PLX108-01 until they are ready to begin screening in the phase 4 continuation study. Screening for the phase 4 continuation study may occur prior to withdrawal from PLX108-01.

Following the last dose of drug, all patients will have the following evaluations:

1. Physical examination including weight (kg) and vital signs (sitting blood pressure, pulse rate, and respiratory rate, and oral temperature [°F]).
2. Standard 12-lead ECG to determine QTcF.
3. Clinical laboratory evaluation (hematology, chemistry, urinalysis, serum pregnancy test (women of child-bearing potential).
4. ECOG Performance status assessment.
5. For patients enrolled after the implementation of Amendment 8, collect the six (6) completed NRS for PVNS Symptoms questionnaires and give the patient another one of the questionnaires to complete predose. NOTE: the NRS for PVNS Symptoms questionnaire to be completed in the clinic is exactly the same as the other 6 daily questionnaires.
6. For patients enrolled after the implementation of Amendment 8, then give the patient the Western Ontario and McMaster Universities Osteoarthritis Index (WOMAC) questionnaire to complete predose. NOTE: At each of the applicable visits, sites should refrain from providing any interpretation of how the questions should be answered by the patient.
7. Radiographic assessment of tumor burden.
8. Test article compliance.
9. Concomitant medications.
10. Collection of surgical data - If surgical resection of the tumor is performed within 30 days of the last dose of study treatment, details of the surgery and its outcome should be obtained.

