15.0 DISCONTINUATION OF TREATMENT AND WITHDRAWAL OF PATIENTS

The reasons a patient may discontinue or be withdrawn from the study include, but are not limited to, adverse event, disease progression, patient request, protocol violation, patient noncompliance, study termination by the Sponsor, and subject transition to commercial pexidartinib (Turalio™). When a patient discontinues or is withdrawn, the investigator will notify the Sponsor and should perform the procedures indicated in the End of Study visit column in the study flow chart 7–30 days after the last dose of study drug and prior to initiation of any new anti-cancer therapy. Follow-up information will be obtained for patients who discontinue their participation in or are withdrawn from the study. Patients withdrawn from the study will be replaced at the discretion of the medical monitor and the investigator. Test article administration may be discontinued for an adverse event or at the discretion of the investigator.

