18.0 SAFETY EVALUATION

Routine safety and tolerability will be evaluated from the results of reported signs and symptoms, scheduled physical examinations, vital sign measurements, 12-lead ECGs (including QTc intervals), and clinical laboratory test results.

Safety data will be reviewed by the investigator and the medical monitor. Safety of pexidartinib will be established after 28 days of dosing at the previous dosage group before the next higher dose is initiated.

More frequent safety evaluations may be performed if clinically indicated or at the discretion of the investigator. All AEs will be recorded from the time the patient receives the first dose of study drug until the patient's End of Study visit.

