26.2 Recording and Reporting

A patient's AE or SAE can occur from the time the patient receives the first dose of study drug until the patient's End of Study visit.

The investigator must follow-up on all drug-related AEs, SAEs, and other reportable information until the events have subsided, returned to baseline, the patient has initiated any other anticancer treatment, or in case of permanent impairment, until the condition stabilizes.

All AE and SAEs must be recorded on source documents. All AEs and SAEs for patients who are not screen failures will be recorded in the CRFs.

AEs should be based on the signs or symptoms detected during the physical examination and on clinical evaluation of the patient. In addition to the information obtained from those sources, the patient should be asked the following nonspecific question: "How have you been feeling since your last visit?" Signs and symptoms should be recorded using standard medical terminology.

Any unanticipated risks to the patients must be reported promptly to the IRB/IEC.

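### The End of Study visit has two conflicting windows for extension patients who stop pexidartinib, and recording of new adverse events ends at that visit

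*Combined protocol and SAP*

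**What the plan says.** Three places in the current text time the End of Study visit for extension patients who come off pexidartinib.

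- Extension flow chart, footnote 3: "End of Study or early withdrawal procedures should be completed 7-30 days after the last dose of study drug".
- Section 15.0 sends the investigator to the "End of Study visit column in the study flow chart 7–30 days after the last dose of study drug".
- Section 14.8, heading: "last + 30 ± 7 days for all other subjects". The table of contents repeats it.

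Footnote 3 and Section 15.0 also require the visit before any new anticancer therapy starts.

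Patients who stay on the drug are handled separately. In footnote 3 the visit is "or on the date of last dose of study drug for all subjects that enroll in the phase 4 continuation study", and patients going to commercial drug are seen before that transition. Section 14.8 likewise places both groups at last dose.

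The same visit closes AE recording. Section 18.0: "All AEs will be recorded from the time the patient receives the first dose of study drug until the patient's End of Study visit". Section 26.2 sets the same limit: "AE or SAE can occur from the time the patient receives the first dose of study drug until the patient's End of Study visit".

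Section 14.9, on the 12-week follow-up, covers imaging and surgical data only, and its flow chart column has no AE mark. The dose escalation flow charts carry a third wording: end-of-treatment procedures within 30 days of last dose.

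**The concern.** A mismatch between visit windows is often only a scheduling nuisance. Here the visit date is also the cut-off for new AEs and SAEs, so the mismatch reaches the safety data. An event that first appears on day 15 after last dose is outside the recording period if the visit took place on day 10, and inside it if the visit took place on day 25. Each visit complies with at least one text.

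Section 24.1 counts patients with each event and reports percentages. It sets no post-dose window and makes no adjustment for length of observation. The protocol uses the term treatment-emergent without defining it in days after last dose. Unequal capture therefore passes straight into the reported incidence, and a shorter period can only lower the count of new events.

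Late-onset events matter for this drug. Section 14.7 allows up to 4 weeks for raised liver tests to recover and asks for long-term follow-up of suspected cholestatic injury.

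**Working it through.** The plan gives no figure of its own here, so the check compares the stated windows and then illustrates the effect.

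**Inputs.** Window A, days 7 to 30 (footnote 3, Section 15.0). Window B, 30 − 7 = 23 to 30 + 7 = 37 (Section 14.8 heading). AE cut-off: the visit itself (Sections 18.0, 26.2).

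**Which visits comply.**

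| Visit day after last dose | Footnote 3 and Section 15.0 | Section 14.8 |
|---|---|---|
| 7–22 | complies | breaches |
| 23–30 | complies | complies |
| 31–37 | breaches | complies |

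**Spread of the capture period (latest day / earliest day).**

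- Window A alone: 30/7 = 4.3
- Window B alone: 37/23 = 1.6
- Either text followed: 37/7 = 5.3
- Overlap only: 30/23 = 1.3

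Most of the spread comes from the width of window A. Choosing one window would remove the contradiction, but if the 7–30 day window were kept, capture would still vary 4.3-fold. That is why the cut-off has to be separated from the visit.

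**Illustration.** The documents give no rate of new post-treatment AEs. Assume a constant hazard with probability r of a first new event per 30 days. The chance of capture by day d is 1 − (1 − r)^(d/30).

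| Assumed r | Day 7 | Day 23 | Day 30 | Day 37 | Day 37 minus day 7 |
|---|---|---|---|---|---|
| 5% | 1.2% | 3.9% | 5.0% | 6.1% | 4.9 points |
| 10% | 2.4% | 7.8% | 10.0% | 12.2% | 9.8 points |
| 20% | 5.1% | 15.7% | 20.0% | 24.1% | 19.0 points |

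These figures concern events that begin after the last dose. They do not describe whole-study AE incidence.

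**Share of total observation.** The 23 days between a day-7 and a day-30 visit, as a share of treatment time plus 30 days (28-day cycles, illustrative durations):

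- 2 cycles: 23/(56 + 30) = 27%
- 6 cycles: 23/(168 + 30) = 12%
- 40 cycles: 23/(1120 + 30) = 2%

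The effect on overall incidence is largest for patients who stop early.

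**The case against.** **Sites are bound by the whole protocol, and days 23 to 30 satisfy all three places.** This is correct, and it limits the claim: a reader might infer that follow-up actually differs five-fold between patients, but 5.3 is only the ratio of the latest day in one text to the earliest day in another. The overlap does not fully settle the matter. Nothing says which text governs. A patient starting new anticancer therapy before day 23 must be seen earlier under footnote 3 and Section 15.0, which Section 14.8 does not allow for.

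**Safety follow-up does not stop at the visit.** This stands. Section 26.2 keeps drug-related AEs, SAEs and other reportable information under follow-up until they subside, return to baseline or stabilise, or until other anticancer treatment begins. Pregnancies are reportable up to 3 months after treatment. Section 14.7 continues liver monitoring after discontinuation. Only events with first onset after the visit are lost. Section 15.0 does promise follow-up information on withdrawn patients, but it names neither AEs nor a duration.

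**An early visit does not move the off-treatment scan.** This also stands. Footnote 11 times that scan separately, at about 30 days and 12 weeks, and footnote 4 accepts scans from other sources within 24 weeks if one is missed.

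**Patients seen early need not be the sickest.** The documents give no support for that inference. The rule that the visit precede new therapy has a sound purpose: later events would be confounded.

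**The study is open-label and single-agent, with descriptive analysis.** True, so no randomised comparison is biased. The reported AE percentages still depend on the cut-off.

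**Conclusion.** The contradiction is real and sits in current operative text. For extension patients who stop pexidartinib, new AEs and SAEs may be captured for 7 to 37 days after last dose with both texts in force, or 7 to 30 days under footnote 3 alone, and Section 24.1 does not allow for the difference. The direction of the effect is clear: earlier visits record fewer new events. Its size is not known, because the documents give neither actual visit dates nor a post-treatment event rate. The capture probabilities above rest on an assumed constant hazard.

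The point does not extend to patients whose visit falls at last dose or before transition because they continue the drug. It does not show an observed five-fold spread, loss of follow-up for known events, a shifted scan, or selective under-reporting in sicker patients. The documents do not show which visit window is intended, so the passages must be reconciled. The change is worth making because it is cheap and makes AE capture uniform.

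**What to change.** 1. State one End of Study window in extension flow chart footnote 3, the Section 14.8 heading (with the table of contents) and Section 15.0. Reconcile the wording in the dose escalation flow charts at the same time, since Sections 18.0 and 26.2 apply to all cohorts.
2. In Sections 18.0 and 26.2, separate the AE/SAE recording cut-off from the visit date. Set one fixed number of days after last dose for patients who stop pexidartinib; day 30 lies in both extension windows. Where the visit came earlier, complete the recording by telephone.
3. Keep the cut-off at transition for patients who continue in the phase 4 study or on commercial drug. Otherwise AE collection would run into the next study or into commercial treatment.
4. Flag events that begin after the start of a new anticancer therapy, so that they can be tabulated separately.
5. Use the same cut-off in Section 24.1, and add adverse events to the Section 14.8 procedure list, which omits them although the flow chart marks them at that visit.

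The cost is amendment wording and one short call for each patient seen early. Telephone AE check-ins already exist in the protocol for visits after Cycle 40. The downside is that some added events will be confounded by new therapy, which item 4 addresses. For patients already past the visit, the report can show the interval from last dose to End of Study beside the AE tables.

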6.0 INTRODUCTION

6.1 Background

Kinases play a ubiquitous role in the signaling pathways for proliferation, metastasis, and survival of most tumor types. Pexidartinib is a potent and selective inhibitor of Fms (the receptor for macrophage-colony stimulating factor, M-CSF), Kit (the receptor for stem cell factor, SCF) and oncogenic Flt3 (the receptor for Flt3 ligand). Therefore, it has the potential to treat cancers through multiple mechanisms. For example, somatic activation of Kit and Flt3 has been well-documented in a number of cancers. Beyond the direct dependence of tumors on these oncogenic drivers, Fms and Kit are regulators of key components of the tumor microenvironment, namely macrophages, osteoclasts, and mast cells. Therefore, pexidartinib has effects on multiple aspects of tumorigenesis, including proliferation, intravasation, extravasation, and survival of metastases. The inhibition of these activities by pexidartinib has been characterized in cellular and in vivo assays. The pharmacologic efficacy demonstrated to date and the therapeutic promise support further development of pexidartinib as an anti-cancer therapeutic.

Pexidartinib is a novel, orally active, small molecule inhibitor that targets Fms, Kit and oncogenic Flt3, but remains highly selective versus other kinases. The potent inhibition of these three kinases can be exploited to attack tumors via different mechanisms: 1) directly inhibiting oncogenic drivers such as oncogenic Kit and Flt3 mutant proteins, 2) inhibiting paracrine loops between stromal cells and tumors, 3) blocking migration and angiogenesis, and 4) disrupting osteolytic metastases.

Tumor control due to blockade of Kit mutations has been validated in the clinic through the established efficacy of imatinib and sunitinib in gastrointestinal stromal tumors (Fletcher 2007). Clear tumor responses in patients with acute myelogenous leukemia (AML) using inhibitors of mutant Flt3 have also been reported, although none of these inhibitors has yet been approved to treat AML (Tam 2008). Pexidartinib may afford an advantage over other compounds in that very few ‘off-target’ kinases are inhibited. Indeed, pexidartinib preferentially inhibits oncogenic Flt3 versus the wildtype protein, providing promise for a wider therapeutic potential.

The efficacy of osteoclast antagonists such as bisphosphonates in preventing bone fractures and pain resulting from osteolytic metastases has been recognized for some time (Kohno 2008). Osteoclasts require the parallel activation of the RANK-L and Fms pathways for activity and survival. Recently, RANK-L antagonists have demonstrated efficacy to prevent bone destruction in preclinical models, and efforts to validate this in the clinic are well underway (Lipton 2008). As a potent inhibitor of Fms, the anti-osteoclast effects of pexidartinib that are seen in vitro and in vivo provide an alternative mechanism to block bone destruction and consequent pain.

More recently, an important role for tumor infiltrating macrophages in tumor progression has pointed to Fms as a key target in multiple tumor types (Coffelt 2009). The pro-tumorigenic role of CSF-1 and Fms is strongly supported by a wealth of studies demonstrating that CSF-1 levels predict a poor outcome in a variety of oncology indications, including breast, ovarian, non-small

cell lung, and colorectal cancers. Further strengthening the fundamental tumorigenic role of Fms is a key study showing that mice defective in CSF-1 are protected against tumor metastases.

Accordingly, treatment of breast cancer xenografts with anti-sense, antibodies or siRNA to CSF-1 suppresses tumor growth. The mechanism for this inhibition relates in part to a paracrine loop that links CSF-1 secreting tumor cells with EGF-secreting macrophages (Pollard 2008). Furthermore, a growing body of literature has now linked macrophages to angiogenesis (Coffelt 2009). One final aspect to tumorigenesis also implicates Fms, namely its role in the terminal differentiation of osteoclasts (Tanaka 2007). Coupled with the reported efficacy of bisphosphonates and RANK-L antagonists in tumor models, the anti-osteoclast activity of Fms inhibition should supplement the anti-macrophage mediated tumor suppressive potential. Taken together, this information provides a rationale for the role of Fms as a potentially important cancer target.

Finally, mast cells also comprise an important fraction of the microenvironment of certain tumors. For example, in plexiform neurofibromas that cause significant morbidity in patients with neurofibromatosis type 1, a paracrine loop between mast cells and Schwann cells has been demonstrated in preclinical models (Yang 2008). Subsequently, pexidartinib has shown preliminary efficacy to reduce development of plexiform tumors in a mouse model of NF1.

6.2 Pharmacodynamics

In brief, biochemical data support Fms, Kit and oncogenic Flt3 as key targets of pexidartinib. Consequently, proliferation of cell lines that alternatively depend on M-CSF, SCF, or endogenous Flt3 that is oncogenically activated by internal tandem duplications (Flt3-ITD) is inhibited at IC₅₀ values below 1 μM. Furthermore, M-CSF-induced autophosphorylation of Fms and SCF-induced autophosphorylation of Kit are potently inhibited by pexidartinib. By contrast, Flt3-ligand induced autophosphorylation of Flt3 and Flt3-ligand induced proliferation of cells are only weakly inhibited by pexidartinib, suggesting preferential inhibition of the oncogenically-activated kinase. Finally, the RANK-L and M-CSF-dependent differentiation of osteoclast precursors is also potently inhibited by pexidartinib. These in vitro effects translated to effects in a variety of in vivo models designed to test the effects of pexidartinib on Fms-dependent proliferation, Fms-dependent osteoclasts differentiation, and Flt3-ITD dependent tumor growth.

6.2.1 In Vitro Pharmacodynamics

Pexidartinib shows significant selectivity versus a panel of over 200 kinases. Fms, Kit, and activated Flt3 appear to be the most sensitive target kinases, with IC₅₀ values of 17, 12, and 9 nM, respectively (see Table 1).

Table 1: IC₅₀ Values of Pexidartinib Against Selected Kinases

Kinase	Fms	Kit	Flt3	Kdr	Lck	Flt1	TrkC
Pexidartinib	17 nM	12 nM	9 nM	213 nM	860 nM	880 nM	890 nM

Kdr kinase activity is only modestly affected, and other kinases tested are even less sensitive to pexidartinib. While physiologic effects due to the inhibition of Fms and Kit are expected, the selectivity of pexidartinib suggests that minimal off-target effects should be observed. When screened against a broad panel of additional kinases, IC₅₀ values were >1 μM for all, with the majority >10 μM.

Pexidartinib also demonstrated negligible activity in a standard Novascreen panel screen. This is a screen for off-target activity against a broad array of 71 targets in 8 families (Neurotransmitter-related, Steroids, Ion Channels, Nitric Oxide, Prostaglandins, Growth Factors, Brain/Gut Peptides, and Enzymes). At a concentration of 10 μM serum-free, all results were within 40% of Baseline, indicating no relevant off-target activity.

M-NFS-60 cells and BAC1.2F5 cells are mouse cell lines that require M-CSF to proliferate, and Mo7E cells are human cells that require SCF to proliferate. The ligand dependent proliferation of these cells is inhibited by pexidartinib with IC₅₀s of 0.33, 0.23 and 0.31 μM, respectively. In THP-1 cells, Fms autophosphorylation induced by M-CSF can be inhibited by 7 nM concentrations of pexidartinib. In Flt3-ITD-expressing MV4-11 cells, ligand-independent autophosphorylation of Flt3 is potently inhibited by pexidartinib with an IC₅₀ of 26 nM. By contrast, in RS4:11 cells, Flt3 autophosphorylation can be induced by Flt3 ligand and this autophosphorylation requires high levels of pexidartinib (1500 nM) for inhibition. This weak inhibition of Flt3-ligand effects suggests that pexidartinib binds only weakly to unactivated Flt3. Finally, human osteoclast precursor cells can be induced to differentiate in to mature osteoclasts by the combination of RANK-L and M-CSF. Pexidartinib inhibits this osteoclast differentiation with an IC₅₀ of 33 nM.

